### **4.4 Subject Completion/Withdrawal**

Subjects may withdraw from the study at any time without prejudice to their care.

---

## 5 STUDY EVALUATIONS AND MEASUREMENTS

### 5.1 Screening and Monitoring Evaluations and Measurements

#### 5.1.1 Medical Record Review

Variables to be abstracted into the REDCap™ database from the medical charts of ALL cohort patients enrolled at each site will include the following:

- Date of study days
- Weight
- Height
- Demographics (sex, race, ethnicity)
- Underlying conditions (e.g., type of leukemia)
- Co-morbid conditions
- Laboratory values (e.g. Creatinine, AST, ALT, Bilirubin, coagulation profile, WBC, platelets)
- Level of illness (e.g. need for ICU admission, intubation, vasopressors)
- Immune suppression therapies most recently associated with the qualifying condition
- Vital status at last date of follow-up
- Vaccination records
- Social determinants of health-related data (e.g. block group number (zip code plus 4) of residence, insurance type) (Optional – to be collected only for ALL cohort patients/families who consent to having these data collected and for healthy control patients)

Results from the following reports will be collected when available

- Pathology reports
- All radiology reports
- Microbiology results
- Non-culture mycology testing (e.g., Histoplasma urine antigen)
- Interventional radiology reports
- Surgical and procedural reports (e.g. bronchoscopy, eye and sinus exams)

---

Variables to be collected for matched healthy control cohort patients selected from CHOP's PeRC include:

- Date of study days (assigned to mirror the follow-up period of the matched ALL cohort patients)
- Demographics (sex, race, ethnicity, age)
- Underlying conditions
- Co-morbid conditions
- Laboratory values (e.g. Creatinine, AST, ALT, Bilirubin, coagulation profile, WBC, platelets)
- Details of any infection-related healthcare encounters occurring during the assigned study period (e.g. date of infection(s), lab results related to infection, physical examination findings, medications)
- Level of illness (e.g. need for ICU admission, intubation, vasopressors)
- Vaccination records
- Social determinants of health-related data (e.g. block group number (zip code plus 4) of residence, insurance type)

Results from the following reports will be collected when available and related to infections occurring in the study follow-up period:

- Pathology reports
- All radiology reports
- Microbiology results
- Non-culture mycology testing (e.g., Histoplasma urine antigen)
- Interventional radiology reports

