**Study Measures:**

Aim 1 will capture any infection documented at any inpatient or outpatient encounter documented by the managing medical team in the first year after completing ALL chemotherapy. An incident infection rate will be calculated for the cohort and compared with that of age- and sex-matched healthy controls during the same time period. The secondary aim will assess the seroprevalence for pneumococcus, varicella and measles among study subjects at approximately 3, 6, and 12 months after completion of therapy. This aim will also describe B and T lymphocyte subset recovery at these same timepoints. The outcomes for Aim 1 and Aim 2 will be described by certain demographic characteristics and underlying diagnoses, as well as ALL treatment protocol. Additionally, laboratory reports will be prospectively collected. These data will serve to define the infection rate in the first year after completing ALL chemotherapy and inform immune recovery overall and to specific vaccine preventable illnesses (i.e. varicella, measles, and pneumococcus).

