At the end of 2024, the Children's Oncology Group reported data from a randomized controlled trial revealing improved effectiveness of ALL chemotherapy regimens inclusive of the novel biological agent blinatumomab. The improved outcomes of patients receiving ALL chemotherapy inclusive of blinatumomab has led to immediate transition to this regimen as standard of care for most patients with ALL. While blinatumomab may have improved effectiveness for cure of cancer it may alter immune reconstitution trajectories in the survivorship period. Because most of this study cohort was enrolled prior to the institution of blinatumomab as standard of care, it is uniquely positioned to now enroll ALL survivors that have or will have received blinatumomab as part of their chemotherapy

---

regimen. Including blinatumomab recipients will provide exploratory data on potential differences in immune reconstitution between patients receiving this new standard of care relative to prior standard of care ALL chemotherapy regimens.

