### **6.3.4 Control of Bias and Confounding**

For Aim 1, patients will be contacted once monthly for symptom reporting. Capture of the primary outcome will be dependent on completion of study visits, phone calls and complete data collection from the medical record. Accordingly, study procedural protocols will be implemented to ensure systematic approach for each enrolled subject. We will also develop a database that will inform a systematic approach to medical record review. This is a descriptive study and thus is not vulnerable to confounding.

To control for possible confounding in the comparison of infection incidence rates of ALL patients to those of healthy control patients, all healthy control patients will be matched to ALL cohort patients based on both age and sex, and controls will be assigned the same one-year “follow-up” period as those of their matched ALL cohort patients, to account for seasonal variation in infection rates as described above. Demographic data and vaccination histories

will be collected as outlined above for both ALL cohort patients and healthy controls to monitor for balance with respect to these important factors. Healthy control patients will be included only if they do not have pre-existing medical conditions that might put them at increased risk for infection to ensure assembly of a healthy cohort that most closely mirrors the general population of healthy children. Further, to reduce the risk of selection bias in the healthy control cohort, a waiver of consent and HIPAA authorization will be requested for these patients.

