## 7 STUDY ADMINISTRATION

### 7.1 Data Collection and Management

Data elements for this study will be obtained from outpatient and inpatient medical records managed at the local sites where subjects will be enrolled. Data will also be collected regarding specimen collection and the results of specimen processing. Data will be captured in a REDCap™ database. The data will be gathered and entered by trained data abstractors at the participating sites. Categories of data captured from the health records include, but are not limited to: demographics, baseline characteristics, comorbidities, laboratory results, clinical outcomes, medications received, and imaging, microbiology and pathology results as outlined in section 5.1.1.

The REDCap™ Database will be hosted by CHOP. REDCap™ is a software toolset and workflow methodology that supports the electronic collection and management of research and clinical trial data and relies on a thorough study-specific data dictionary defined in an iterative self-documenting. REDCap™'s Data access group function allows for confidential data entry and storage from multiple sites. At the time of enrollment and data entry initiation a unique study identifier will be assigned to each subject. Each enrolling site will maintain its own master list that will capture the local medical record number and the unique study identifier for enrolled subjects. Only study personnel approved at that site will have access to the site master list. The master list will be maintained in case there are any data fidelity issues in REDCap™ that would require re-abstraction of data. Access of members of the research team to any patient identifiers will be limited to the minimum necessary to carry out the proposed research. In addition, research material will be accessible only to members of the investigative team that have completed all required trainings in the Protection of Human Subjects. Individual site abstractors will only have access to their own site's data, not the data of the entire study from all centers. Study personnel at CHOP will have access to the entirety of the REDCap™ database for the purposes of database management, data cleaning, and data analyses.

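### The blinatumomab comparisons are planned as crude contrasts, with no treatment-risk variable listed, while Section 6.3.4 rules out confounding

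*Combined protocol and SAP*

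**What the plan says.** **Comparisons.** Section 2.1 (Aim 1 sub-aim) sets infection incidence in blinatumomab recipients against that in non-recipients. Section 2.2 does the same for the immune markers of Aim 2. Section 3.1 plans 20-25 recipients among about 115 enrolled, and Section 1.2 calls the resulting data exploratory.

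**Analysis.** Section 6.3.2 generates an infection rate for each group. Section 6.3.3 describes seroprevalence for each group. Neither names an adjustment or stratification factor for the contrast.

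**Bias.** The first paragraph of Section 6.3.4 ends: "This is a descriptive study and thus is not vulnerable to confounding". The next paragraph does discuss control of confounding, but only for ALL patients against matched healthy controls.

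**Data.** The only treatment item in the ALL-cohort list of Section 5.1.1 is "Immune suppression therapies most recently associated with the qualifying condition". Leukemia type is given as an example of an underlying condition. Treatment protocol, risk arm and a blinatumomab field are not named. The Abstract (Study Measures) says that the outcomes of both aims "will be described by certain demographic characteristics and underlying diagnoses, as well as ALL treatment protocol", but Sections 6.3.2 and 6.3.3 do not carry the by-protocol description forward.

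**The concern.** A rate or proportion for a single cohort can be reported without any question of confounding. A comparison of treated with untreated patients cannot, and the sub-aims make such a comparison.

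The groups have reasons to differ apart from blinatumomab:

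- **Risk group.** Section 3.3.1 accepts B or T ALL of any risk group. The randomized trial cited in Section 1.2 was, by its title in Section 9, in standard-risk B-cell ALL. Receipt may therefore follow risk group, and with it the intensity of the other chemotherapy.
- **Enrollment period.** Section 1.2 says that "most of this study cohort was enrolled prior to the institution of blinatumomab as standard of care", so recipients will tend to be later enrollees. Healthy controls are matched on follow-up period; recipients and non-recipients are not matched to each other.

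At stake is what the sub-aims can say. Section 6.4 expects the immune-function data to inform the need for revaccination. A crude difference would invite a reading about blinatumomab when it could reflect the rest of the regimen.

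**Working it through.** The plan gives no sample size, power or effect figure for the blinatumomab contrasts (Table 1 concerns ALL against healthy controls), so there is no figure to reproduce. The check sets the text side by side and then illustrates the scale.

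**Text**

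| Question | Where | Answer |
|---|---|---|
| Is there a comparison by blinatumomab receipt? | 2.1, 2.2 | Yes, for both aims |
| Is risk group restricted at entry? | 3.3.1, 3.3.2 | No |
| Is protocol or risk arm a listed variable? | 5.1.1 | No |
| Is adjustment or stratification planned? | 6.3.2, 6.3.3 | No |
| Is confounding of this contrast acknowledged? | 6.3.4 | No; healthy-control comparison only |

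**Scale of confounding (all inputs assumed)**

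Let p1 and p0 be the shares of recipients and non-recipients treated on high-intensity arms, and k the infection-rate multiplier of such arms. With no blinatumomab effect, the crude ratio is [1 + p1(k − 1)] / [1 + p0(k − 1)]. Take p1 = 0.20 and p0 = 0.50:

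- k = 1.3: 1.06 / 1.15 = 0.92
- k = 1.5: 1.10 / 1.25 = 0.88
- k = 2.0: 1.20 / 1.50 = 0.80

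The direction is also assumed. With the shares exchanged, the ratios become 1.15 / 1.06 = 1.08, 1.25 / 1.10 = 1.14 and 1.50 / 1.20 = 1.25.

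**Precision, for comparison**

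Inputs: 110 evaluable patients (Section 3.2.2), one year of follow-up each, and 1.88 events per person-year in non-recipients (Section 6.4 gives this for the ALL cohort as a whole). With overdispersion φ, SE(ln IRR) = √{φ[1/(n1·r1) + 1/(n0·r0)]} and power = Φ(ln IRR / SE − 1.96).

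Example with 25 against 85, φ = 1 and IRR 1.494: expected events are 25 × 1.88 × 1.494 = 70.2 and 85 × 1.88 = 159.8; SE = √(1/70.2 + 1/159.8) = 0.143; ln 1.494 = 0.401; 0.401/0.143 − 1.96 = 0.84, which is 80% power.

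| Recipients / non-recipients | φ = 1 | φ = 2 | φ = 3 |
|---|---|---|---|
| 20 / 90 | 1.53 | 1.77 | 1.97 |
| 25 / 85 | 1.49 | 1.72 | 1.90 |

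These are the rate ratios detectable with 80% power. The illustrated bias is smaller than any of them. It would shift the estimate, and could add to or hide a real difference, but would seldom stand out alone.

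**The case against.** **The contrasts are exploratory.** True. No test or model is specified for them, so no planned analysis fails. This limits the severity. It does not make the sentence in Section 6.3.4 correct for a comparison, and an exploratory estimate still needs its main alternative explanation stated.

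**The list in Section 5.1.1 is not exhaustive.** Also true. It also omits age, end-of-therapy date and infection events for the ALL cohort, all of which other sections use. Section 7.1 says "Categories of data captured from the health records include, but are not limited to" and names "clinical outcomes, medications received, and imaging, microbiology and pathology results as outlined in section 5.1.1". Treatment history is chart data and can be recovered. Leukemia type is listed and gives a partial handle. What remains is that no section names risk arm or protocol as a variable to be collected uniformly at seven sites, and none uses it in the blinatumomab contrasts.

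**A stronger reading is tempting.** From the words on most recent therapy, a reader might infer that blinatumomab given earlier in treatment is missed, so that recipients cannot be reliably identified. The documents do not support this. Section 3.3.1 defines the sub-cohort by receipt within ALL chemotherapy, Sections 6.3.2 and 6.3.3 group by receipt, and Section 7.1 captures medications. The phrase can also mean the up-front ALL regimen as a whole. Nor does any section say that earlier enrollees are counted as non-recipients by default.

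Even if some recipients were missed, the dilution would be modest. With 25 recipients, 85 non-recipients and a true ratio of 2.0 (assumed), counting 10% of recipients (2.5) as non-recipients gives 2 / [(85 + 2 × 2.5)/87.5] = 1.94. Counting half (12.5) gives 2 / [(85 + 2 × 12.5)/97.5] = 1.77.

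**Conclusion.** The concern holds for confounding. The plan makes two comparisons by blinatumomab receipt, reports them crudely, lists no treatment-risk variable, and carries a general statement that excludes confounding. As written, a difference in treatment intensity cannot be told apart from a blinatumomab effect using the listed items.

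The size is unknown. The range of 0.92 to 0.80 for a true null rests on an assumed 20% against 50% split and assumed multipliers of 1.3 to 2.0; neither these nor the direction comes from the documents. Against contrasts that detect ratios of only about 1.5 to 2.0, this is a matter of interpretation and does not threaten the study's primary result.

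It should be changed, because the correction is cheap and alters what the sub-aims can conclude.

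**What to change.** 1. **Section 6.3.4:** delete the sentence that excludes confounding. State that the blinatumomab contrasts are exploratory and open to residual confounding, including by treatment risk group and enrollment period.
2. **Section 5.1.1:** list ALL treatment protocol, risk arm and blinatumomab receipt at any time in ALL therapy, for every ALL-cohort patient, including those already enrolled.
3. **Sections 6.3.2 and 6.3.3:** report the blinatumomab contrasts within or adjusted for risk arm and age, beside the crude results. Add the by-protocol description promised in the Abstract.
4. **Aim 2b:** with about 40 patients and up to 10 recipients (Section 5.1.2.1.3), displays labelled by risk arm are enough.

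The cost is one short REDCap form, back-abstraction of about 110 charts already under review, and a few sentences of text. It is best done before the database is closed. With 20-25 recipients, only one or two factors can be adjusted for, and the intervals will be wider. Where a risk arm has almost no recipients, show the table by arm without an adjusted estimate.

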### **3.2 Total Number of Study Sites/Total Number of Subjects Projected**

#### **3.2.1 Duration of Study Participation**

Patients will be followed from the date of enrollment until the first of the following events: approximately one year from completion of therapy, loss to follow-up or death.

Data abstraction from the medical record will be used to determine their end of therapy date. Their medical record will also be examined to collect specified relevant data related to reported infectious history as well as vaccination history. The in-person enrollment visit will require approximately one-hour of direct contact with the patient and caregiver to obtain consent (and when necessary, assent) and to complete the enrollment encounter. Once enrolled, followed by in-person visits at approximately 3, 6, and 12 months. At these visits an interim infectious history will be obtained and patients will have blood drawn for research assays as detailed below. These visits and the associated blood draw will be aligned with regularly scheduled oncology visits. The blood specimen will be drawn by the oncology nursing team and/or phlebotomy and whenever possible will be obtained at the same time as a clinical blood draw. Between in-person visits, study staff will contact caregivers for enrolled patients via phone call, text message, or email (as preferred by caregiver) to capture interim infection events. If text message or email is used to contact caregiver, but additional information is needed, a phone call will be made when necessary.

At the end of participants' study follow-up periods, age- and sex-matched healthy control patients will be identified from the CHOP Pediatric Research Consortium (PeRC) for comparison. Three controls will be randomly selected from a list of otherwise healthy individuals with similar age and sex and matched to each ALL patient enrolled. Infection events will be captured for these controls during the same time period the study participant was followed to compare the rate of infection events in the post-ALL therapy cohort with that of matched healthy controls.

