### 6.3 Statistical Methods

#### 6.3.1 Baseline Data

Baseline and demographic characteristics will be summarized by standard descriptive summaries. Categorical variables will be summarized by frequencies while continuous variables will be summarized by using mean, standard deviation, median, twenty-fifth and seventy-fifth percentiles, minimum and maximum.

#### 6.3.2 Analysis of Aim 1

Aim 1 (total number of unique infections identified within the first year after completing chemotherapy) will be reported as a rate per 1000 follow-up days. This rate will be reported for the entire cohort, by study site, and by demographics (e.g., age, race, gender). This outcome will also be reported within subsets of infection type (i.e., microbiologically documented infections and bacterial sinopulmonary infections) also reported as a rate per

---

1000 follow-up days for the entire cohort, by study site and by specific demographic variables. All infection rates will be reported as a post estimate with 95% confidence intervals. Patients will be censored at time of lost to follow-up or death.

Infection rates for enrolled patients will also be compared to those of controls matched on age and sex selected from the CHOP Pediatric Research Consortium (PeRC). Three healthy controls will be selected for each participant for a case to control ratio of 1:3. Control patient infection data will be obtained for the same follow-up time period as that of the matched case patient in order to match risk for infection from seasonal pathogens (e.g., if a case patient completed ALL therapy and enrolled in the study in January 2023, infection data for the matched controls would be collected from January 2023 through December 2023, the same follow-up period as that of the case patient). All control patients will be randomly selected, and control data will be collected when follow-up is complete for participants in the ALL cohort.

Infection rates will also be generated for patients who received blinatumomab as part of their chemotherapy regimen and those who did not receive blinatumomab.

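### Control follow-up days are assigned rather than observed, and the listed control data cannot support the censoring rule, so any unobserved control time would raise the ALL-versus-control rate ratio

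*Combined protocol and SAP*

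**What the plan says.** The primary objective (Section 2.1) compares the infection rate in ALL patients with that in matched controls. Section 6.3.2 says the infection outcome "will be reported as a rate per 1000 follow-up days", and adds: "Patients will be censored at time of lost to follow-up or death".

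For ALL patients the end of observation can be established. Families are contacted monthly (Section 6.3.4), there are visits at about 3, 6 and 12 months (Section 3.2.1), and the Section 5.1.1 variable list includes "Vital status at last date of follow-up".

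For controls, Section 5.1.1 lists a "Date of study days (assigned to mirror the follow-up period of the matched ALL cohort patients") and "Details of any infection-related healthcare encounters occurring during the assigned study period". The list has no vital status, no last contact and no encounter date unrelated to infection. Section 7.1 describes the source as an automated EHR pull, with chart abstraction where needed.

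The control window is worded in three ways:
- Section 3.2.1: "Infection events will be captured for these controls during the same time period the study participant was followed".
- Section 6.3.2: "Control patient infection data will be obtained for the same follow-up time period as that of the matched case patient".
- Section 6.3.4: "controls will be assigned the same one-year" period as the matched ALL patient.

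No section defines control person-time or says how a control who dies, moves or changes practice is handled.

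**The concern.** A rate needs a denominator of days on which an infection would have been recorded had it occurred. For ALL patients that is roughly what the plan delivers. For controls the days are inherited from someone else's follow-up, and nothing on the list shows whether the child was still receiving care in the network. A control who moves away in month 2 has no further infections in the record and, if the assigned window is used as it stands, contributes ten more months that look infection-free.

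Unobserved control days can add to the denominator but not to the numerator. The distortion therefore runs one way, towards a higher ratio, which is the expected finding. Matching on age, sex and calendar period does not remove it. Departure is plausible for older controls in particular: ALL patients may be up to 31 years old (Section 3.3.1), while their age-matched controls come from a pediatric research consortium.

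**Working it through.** **1. The plan's own figure.** Section 6.4, Table 1 assumes 50 ALL patients, 150 controls, one year of follow-up each, an ALL rate of 1.88 per person-year and two-sided alpha 0.05. The formula is not named. Simulation (20,000 runs per row; counts with variance equal to overdispersion times mean; Wald test on the log rate ratio with robust variance) gives:

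| Overdispersion | Ratio | Stated power | Simulated power |
|---|---|---|---|
| 1 | 1.45 | 80.1% | 81.6% |
| 1.5 | 1.58 | 81.0% | 81.4% |
| 2 | 1.69 | 80.1% | 80.9% |
| 2.5 | 1.81 | 81.2% | 80.8% |
| 3 | 1.90 | 80.0% | 79.2% |

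All rows agree within 2 points. Table 1 is not in error; it takes a full year on every control as given.

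**2. Effect of unobserved control time.** Let u be the share of assigned control person-time on which the child was not under observation. Assume that infections on those days are not captured, that the true rate is the same on observed and unobserved days, and that ALL person-time is fully observed. Then:

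- recorded control rate = true rate × (1-u)
- recorded rate ratio = true ratio / (1-u)

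**3. Values of u.** The documents give none, so these are assumptions. If a fraction f of controls leave at a uniformly random point in the window, each loses half a window on average and u = f/2. Taking f = 5%, 10% and 20%:

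| f | u | 1/(1-u) | True 1.00 reads | True 1.45 reads | True 1.90 reads |
|---|---|---|---|---|---|
| 5% | 2.5% | 1.026 | 1.03 | 1.49 | 1.95 |
| 10% | 5% | 1.053 | 1.05 | 1.53 | 2.00 |
| 20% | 10% | 1.111 | 1.11 | 1.61 | 2.11 |

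**4. Dependence on the care requirement.** Section 3.3.3 admits healthy patients who received care at CHOP from 2022 during the period in which the ALL cohort is followed. It does not say whether this means the individual matched window or the whole study period. On the second reading, a fraction g of controls could be absent throughout their window, and u = 1 - (1-g)(1-f/2). With g = 10% (also an assumption):

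- f = 5%: u = 1 - 0.90 × 0.975 = 12.25%; inflation 1/0.8775 = 1.140
- f = 20%: u = 1 - 0.90 × 0.90 = 19%; inflation 1/0.81 = 1.235

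On the first reading g = 0 and the table in step 3 applies.

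**5. Effect on the test.** With both true rates at 1.88, the log ratio is shifted by d = -ln(1-u), with standard error √{φ[1/(1.88 n₁) + 1/(1.88 n₂(1-u))]}, where φ is the overdispersion parameter. The rejection probability is Φ(d/SE - 1.96) + Φ(-d/SE - 1.96). Example: u = 10%, 110 versus 330, φ = 1 gives d = 0.1054, SE = √(1/206.8 + 1/558.4) = 0.0814, d/SE = 1.294, and a rejection rate of 25.3% against a nominal 5%.

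| u | 110 vs 330, φ = 1 to 3 | 50 vs 150, φ = 1 to 3 |
|---|---|---|
| 5% | 9.7% to 6.6% | 7.1% to 5.7% |
| 10% | 25.3% to 11.6% | 14.1% to 8.0% |

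At u = 0 every cell is 5%.

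**The case against.** A reader might infer that the plan credits every control with a full year of person-time. It does not say so. The control denominator is undefined, and Section 3.2.1 points to the time the ALL participant was actually followed, so a control's window already shortens when the matched patient is censored. The censoring sentence speaks of patients, a word the protocol also uses for controls, and may be meant to cover them. This stands: the defect is a missing definition and missing data, not a wrong rule. But Section 3.2.1 deals only with the ALL patient's departure, and a censoring rule meant for controls still needs data that are not listed.

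A reader might also infer that the control rate is certain to be too low. That is not supported either. If no control time is unobserved, nothing changes, and selecting controls because they received care in the period could push their infection rate up. That second effect is a separate bias of unknown size; it does not make unobserved days observed.

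Three further points have some force:
- The control list is introduced as a list of what is included, so it may not be exhaustive. Vaccination records and chart abstraction could reveal some non-illness contact. Even so, vital status is named for ALL patients and not for controls, and no observability rule is stated.
- Deaths hardly matter: one death among 330 controls removes at most 1/330 = 0.3% of control time. The substance is departure from the network.
- The size is wholly assumed. This is correct, and it is why the result is given as a range.

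**Conclusion.** The point holds in conditional form. Control days are assigned from the matched ALL patient's window, and the listed variables cannot show whether a control was under observation, so censoring at loss to follow-up or death is workable for one arm of the primary comparison and not for the other. To the extent that controls leave the network, the rate ratio is inflated by 1/(1-u): 2.6% to 11% for an assumed u of 2.5% to 10%, and more if the care requirement in Section 3.3.3 refers to the whole study period. Inflation of this order is small beside the ratios of 1.45 to 1.90 that Table 1 treats as detectable, but at u = 10% and the planned 110 versus 330 it would raise the false-positive rate from 5% to roughly 12% to 25%. These figures rest on the assumed u, on the assumptions in step 2 of the working and, for the false-positive rates, on a Wald test that the plan does not name. The planned power is not called into question. The sponsor should act on this before the control data are pulled.

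**What to change.** 1. **Data.** Add to the control EHR pull the dates of all PeRC encounters of any type, including well visits, up to the pull date, plus vital status and any recorded transfer of care.
2. **Eligibility.** State in Section 3.3.3 whether the care requirement refers to the matched window or the whole study period. Require evidence that the control is an active PeRC patient, for example a primary-care encounter in the 12 months before the assigned start date.
3. **Person-time.** Define it in Section 6.3.2: control time runs from the assigned start to the earliest of the assigned end, the control's death, a recorded departure, or the matched patient's censoring date. The last is implied by Section 3.2.1 but should be stated, and the one-year wording in Section 6.3.4 aligned with it.
4. **Sensitivity analysis.** Repeat the comparison in controls with a PeRC encounter of any type both before and after the window, or report the ratio over a stated range of u. The first option needs enough time between window close and the pull, which may be short for controls matched to the last patients followed; the second does not.
5. **Avoid** simply truncating control time at the last encounter. Infections are themselves encounters, so healthy children would lose time preferentially and the control rate would be overstated.

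The cost is a few fields in a pull that is to be run only after ALL follow-up is complete, and one sensitivity analysis. The downside is slightly fewer eligible controls and a rate ratio that may turn out less favourable.
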